This study is aimed at developing a novel intervention for therapy of severe hepatic steatosis in patients with FPLD. The intervention, OCA, is a strong FXR activator and there is emerging evidence of the role of FXR agonists in improving hepatic steatosis from the data obtained in experimental animals and in obese patients with NASH or NAFLD. Thus, this will be the first proof-of-concept study to ascertain the role of OCA in improving hepatic steatosis in patients with FPLD. We will use the state of the art technology of measuring hepatic fat content by proton magnetic resonance spectroscopy. We will also measure plasma FGF19 levels as marker of FXR activation and assess hepatic insulin sensitivity using the robust two-step, euglycemic, hyperinsulinemic glucose clamp technique along with infusion of stable isotope of glucose for measuring glucose turnover.

We are aware of the preliminary data from the FLINT trial of OCA for NASH treatment. However, the mechanisms of hepatic steatosis in patients with lipodystrophies are quite different than those in obese STU062014-033, [name], Form A, Mod_8, 08-02-19

Page 3 of 24

patients with NASH who usually have high circulating levels of free fatty acids and marked upregulation of sterol regulatory element binding protein-1c (SREBP-1c) along with increased *de novo* lipogenesis (50, 51). On the other hand, in a mouse model of CGL, type 1 due to Agpat2 deficiency, *Mgat1* was markedly upregulated in the steatotic liver indicating that hepatic triglyceride synthesis was occurring through an alternative pathway; and a marked increase in hepatic *de novo* lipogenesis occurred without any upregulation of SREBP-1c (52). Similar observations were made in the steatotic livers of CGL, type 2 mice with seipin ablation where the expression of SREBP1c did not change despite increased expression of lipogenic genes such as fatty acid synthase (53). Furthermore, in both the models of CGL, serum levels of free fatty acids were not elevated or were in fact lower than those in the wild type mice (52-54). The transgenic mouse model of FPLD overexpressing the human p.R482Q *LMNA* mutation also develops hepatic steatosis without any increase in basal lipolysis (55). However, the investigators did not study the molecular changes underlying hepatic steatosis in the FPLD mouse model.

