Patients will be educated to maintain their usual physical activities and diet during the study. The subjects will be admitted to the Clinical and Translational Research Center for the baseline evaluations (at the beginning of the two study periods), and at the end of four months during each study period. In some subjects, unable to visit CTRC at the end of 2 months, we will provide kits to them for mailing the blood and urine samples using courier service. We have done such collections successfully in our previous trials of leptin therapy in patients with lipodystrophies.

Justification for the choice of design: We considered both the randomized, parallel design and the cross-over design. In view of the rare prevalence of FPLD, we decided to use the cross-over design. This allows us to achieve more power with fewer patients compared to the parallel design. We do not expect carry over effects of OCA on hepatic triglyceride levels given that there will be a four month wash-out period between the two study periods and an additional 4 month time before determining the end point variable during the second study period. We will attempt to keep the drop-outs to as minimum as possible to achieve maximum out of this design. Our choice of study design was guided by Lagakos's editorial entitled, "Clinical Trials and Rare Diseases" (58).

Primary and Secondary Endpoint Variables: The primary end-point variable will be the reduction in the liver TG content on ¹H MRS. Reductions in the levels of serum alanine and aspartate aminotransferases, gammaglutamyl transpeptidase, triglycerides, insulin and suppression of hepatic glucose output during the low-dose and high-dose insulin infusions during the euglycemic clamp study (measure of hepatic insulin sensitivity) will STU062014-033, [name], Form A, Mod_8, 08-02-19 Protocol version number 1, 08042014

Page 6 of 24

be the secondary end-points of the study. Complete blood counts and serum chemistries will be performed for safety considerations. As an evidence of FXR activation, fasting serum FGF19 levels will be measured. We will also measure liver size using magnetic resonance imaging. These additional tests will be performed at baseline and after 2 and 4 months of therapy.

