Three-Day Food Record: Dietary intake will be assessed by 3-day food record (two weekdays and one weekend day), a valid and reliable method (64). The measure will be taken at baseline and each of the follow-up visits. The participants will be instructed on how to record in detail all the food and drink consumed in the 3-day food record booklet provided. The booklet will be available in both English and Spanish (see Appendix). The participants will also be provided a two-dimensional visual chart of food portions to aid them in estimating portion sizes. Any questionable input or incomplete food entries recorded will be promptly addressed when the subjects return their food records. The food records will be analyzed for nutrient content using the University of Minnesota Nutrient Data System (NDS) for research. The NDS database contains more than 18,000 foods, 8,000 brand name products, and many ethnic foods. The database is continuously updated to reflect newly published or provisional data provided by the United States Department of Agriculture, new analytic data from the scientific literature, and current food composition data for new and reformulated commercial products. The database is also put through rigorous quality control (65). The NDS has the capability of calculating daily totals

Page 8 of 24

and amounts by food groups for 120 nutrients and nutrient ratios. It can also calculate gram weight for individual foods.

Oral Glucose Tolerance Test (OGTT): A 3 hour OGTT will be performed after 10-12 h overnight fast. An intravenous line will be placed for blood drawing. On the day of fasting, patient will have a fasting venous blood sample collected and then will be Instructed to drink the glucose solution (75 g of glucose in 200 ml of water) over a maximum of 15 minutes (ideally within 5 minutes). Time will be noted. Blood tests will be done at half-hour intervals for three hours to check patient's glucose and insulin response. A total of 45 ml blood or 3 tablespoons (for adults) will be withdrawn during this test. For oral glucose tolerance tests, the volumes are adjusted for weight, and the sample frequency and duration are decreased.

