
STU062014-033, [name], Form A, Mod_8, 08-02-19 Protocol version number 1, 08042014

Page 15 of 24

questionnaire on gastrointestinal symptoms, subjects will be asked to undergo a glucose clamp study for which there is a minimal risk of psychological or physical discomfort from fasting and an intravenous saline locks, the risk of hypoglycemia, the inconvenience of time spent and the unlikely risk for bruising, fainting, or infection. Subjects will also have phlebotomy for DNA and genotyping for LMNA, and repeated phlebotomy for which there are the minimal risks of physical and psychological discomfort, the requirement of fasting, and the unlikely risk for bruising, fainting or infection.

The potential risks and discomforts of the evaluation methods being used are: *Magnetic Resonance Spectroscopy (MRS) scans*: requires holding still in a noisy scanner, no radiation risk. *3-day food recalls*: no risk, the inconvenience of the brief time spent. *Quality of life and gastrointestinal symptoms questionnaires*: no risk, the inconvenience of the brief time spent Phlebotomy and line placement for OGTT carries the rare to occasional minimal risk of discomfort, hematoma, infection, fainting and/or vasovagal response. Oral glucose tolerance test carries minimal, occasional risk for nausea and/or vomiting.

Subjects will be asked to undergo phlebotomy for DNA and genotyping for *LMNA*, for which there is the risk of phlebotomy, ,fasting, and the minimal risk of bruising, fainting, infection or hypoglycemia. Subjects will also undergo repeated

routine fasting phlebotomy for which there is a minimal risk of psychological or physical discomfort, the discomfort of fasting, the inconvenience of time spent and the unlikely risk for bruising, fainting or infection.

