Statistical analysis: Descriptive statistics and 95% confidence intervals will be used to summarize responses to OCA and Placebo treatment and treatment differences of this crossover study. For hepatic triglyceride concentration, mixed linear repeated measures models will be constructed to compare OCA versus Placebo after four treatment months and to evaluate treatment sequence effects. Secondary endpoint variables will be FGF19 levels, hepatic insulin sensitivity measurements from the euglycemic, hyperinsulinemic glucose clamp, serum triglycerides, insulin, and aminotransferase levels and will be analyzed with similar mixed linear repeated measures models. Two month treatment response comparisons, gender subgroup interactions, per-protocol hepatic triglyceride concentration responses will be assessed as secondary analyses. The primary and secondary endpoints, which are likely to be skewed, will be log transformed prior to analysis, as appropriate. Nonparametric tests will be implemented, if necessary, to satisfy analysis assumptions. Exploratory analyses: Delta responses (OCA-Placebo) will be computed for primary and secondary variables and the association among the delta variables will be evaluated with Spearman correlation coefficients. A two-sided p value of <0.05 will be considered statistically significant. No interim analysis is planned because of the relatively short study duration and limited sample size. SAS (SAS Institute,

Page 17 of 24

Cary, NC) statistical software will be used; particularly SAS PROC MIXED will be used for repeated measures models. The data will be analyzed according to intention-to-treat principles; our mixed model analysis approach can accommodate certain types of missing data. If a subject is unable to complete or tolerate the intervention in either blinded treatment period, we will continue follow-up if possible or the post-treatment and other final measurements may be made prior to 4 months to minimize missing outcome data.

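### Does the lack of a written clamp procedure leave the hepatic insulin sensitivity endpoint empty, with an unanalysed OGTT in its place?

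*Combined protocol and SAP*

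**What the plan says.** The clamp appears in four places.

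- Section 2 (Background) says that hepatic insulin sensitivity will be assessed with a "two-step, euglycemic, hyperinsulinemic glucose clamp technique along with infusion of stable isotope of glucose for measuring glucose turnover".
- Section 3, under the endpoint variables, makes the secondary endpoint "suppression of hepatic glucose output during the low-dose and high-dose insulin infusions during the euglycemic clamp study".
- Section 9 (Potential Risks) says that "subjects will be asked to undergo a glucose clamp study for which there is a minimal risk", and covers fasting, intravenous locks and hypoglycemia.
- Section 13 lists "hepatic insulin sensitivity measurements from the euglycemic, hyperinsulinemic glucose clamp" among the secondary variables. They are analysed with mixed models like the one for the primary endpoint, log transformed where appropriate, with a nonparametric fallback and a two-sided 0.05 level.

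Section 3 schedules admissions for "baseline evaluations (at the beginning of the two study periods), and at the end of four months during each study period".

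Section 4 describes the history and examination, spectroscopy, liver volume, fasting chemistry with insulin and FGF19, the food record, the OGTT, gene sequencing and safety monitoring. It has no clamp entry. Of the OGTT it says "A 3 hour OGTT will be performed after 10-12 h overnight fast", with half-hourly glucose and insulin samples. The OGTT is in neither the endpoint list of Section 3, nor the analysis of Section 13, nor the benchmarks for success.

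**The concern.** The two tests seem to have opposite gaps: the clamp has an endpoint and a model but no procedure, and the OGTT has a procedure but no endpoint or model. Three further details suggest an incomplete edit.

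- The Section 9 list introduced by "The potential risks and discomforts of the evaluation methods being used are" includes the OGTT ("Phlebotomy and line placement for OGTT carries the rare to occasional minimal risk of discomfort") but not the clamp.
- References 66 to 68, whose titles include the clamp technique and hepatic glucose output, are cited nowhere in the text.
- The figure captions go from Fig. 7 to Fig. 9.

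If the clamp had been replaced, the Section 13 endpoint would have no data and any OGTT index would be chosen after the fact. The OGTT could not stand in for the endpoint as defined, because it does not measure suppression of hepatic glucose output. The domain has some importance: Section 1 notes that the earlier six-week diabetes trial did not directly assess hepatic insulin sensitivity, and Section 12 lists better insulin sensitivity as a possible benefit.

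**Working it through.** The plan states no figure for the clamp, so the check is mainly a comparison of texts.

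**1. Is the clamp still in the trial?** Sections 2, 3, 9 and 13 say or presuppose that it is done. No section removes it or says that the OGTT replaces it. Section 4 is silent, and silence in one section does not cancel four others.

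**2. What is specified and what is not?**

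| Item | Where given |
|---|---|
| Technique: two-step, stable glucose isotope | Section 2 |
| Variable: suppression of hepatic glucose output at low and high insulin | Section 3 |
| Model, transformation, fallback, significance level | Section 13 |
| Main comparison: after four months of each treatment | Section 13 |
| Infusion rates, step durations, tracer dose, output formula | Not given for this trial |

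The only rates in the document, 60 and 120 mU/m² body surface area/min, belong to trial 747-203 and are not adopted here. The missing items are operational. The statistical items are present.

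**3. Does Section 9 contradict itself?** The clamp's risks come in the paragraph just before the list. Leaving the clamp out of the list avoids repetition as plausibly as it signals removal. Risk text exists for both tests, which fits both being performed.

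**4. How strong are the traces of an edit?** The citations run to 65 in the food-record paragraph and resume at 69 in the sequencing paragraph, with the OGTT paragraph between them. References 66, 67 and 68 (three items) are therefore uncited. This fits deleted clamp text but does not show that the clamp itself was abandoned. The missing Fig. 8 caption is weaker evidence, since figures are not reproduced in the available copy.

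**5. How many clamps are involved?** The plan's sample size is 16 evaluable patients, and 16 / (1 − 0.20) = 20 enrolled.

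- Minimum for the four-month comparison: 2 periods × 1 visit = 2 per subject, so 16 × 2 = 32 or 20 × 2 = 40.
- If done at all four admissions (an assumption, because Fig. 5 is not shown): 16 × 4 = 64 or 20 × 4 = 80.

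Both counts assume that every subject has the clamp, whereas Section 9 says only that subjects will be asked. The counts measure workload. They show no bias, loss of power or loss of precision.

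**6. Could the unstated formula tilt the result?** The trial is a double-blind crossover. One calculation applied to all clamps treats a subject's OCA and placebo periods alike. It may change the scale or the noise of the measure, but it gives no way to favour one treatment as long as it is settled before unblinding.

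**7. Is the OGTT without an analysis an error?** The food record also has a procedure and no analysis in Section 13. Section 3 reports unclear diabetes status in 20 of the patients being followed, and entry was widened to diabetes managed by diet or metformin. An OGTT that describes glycemic status would fit, although the document does not state that purpose. The insulin endpoint does not depend on it, because Section 4 takes insulin from fasting samples.

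**The case for a change.** The strongest case for a change is that Section 4 is where staff look for what to do. It gives spectroscopy its field strength, timings and voxel, and liver volume its slice thickness and gap, yet gives the clamp nothing. No clamp operating procedure is referenced. Section 13 also feeds the secondary variables into the exploratory correlations of OCA-minus-placebo differences, so the clamp data would be used more than once. The uncited references sit exactly where a clamp paragraph would be expected.

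Much of this stands. The absence is real and no visible gap in the text explains it. Fig. 5 might show when either test is done, but a schedule would not supply a clamp method. A line confirming the clamp and stating the purpose of the OGTT would make the document tidier. What does not stand is the step from missing detail to missing data. The empty endpoint and the improvised OGTT index both require the clamp to have been dropped, which no sentence says. Followed as written, the protocol calls for the clamp and analyses it by a stated method.

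**Conclusion.** The observation is correct and the consequence does not follow. This is a gap in operational detail for one secondary endpoint, of a kind that the clamp laboratory and the analysts fill sensibly: use the two-step isotope clamp of Section 2, calculate glucose output one way for all studies, and fit the Section 13 model. The OGTT can be reported descriptively, and should not be presented as suppression of hepatic glucose output.

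No effect on bias, power or error rate has been shown. The primary endpoint, the sample size and the benchmarks do not involve either test. The conclusion assumes that the clamp is performed, as Sections 2, 3, 9 and 13 indicate, and that its calculation is fixed while treatment is still blinded. If the clamp had in fact been abandoned, the endpoint would simply have to be reported as not collected. The document gives no ground for presuming that.

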Fig. 4 Hepatic triglyceride content during the cholic acid study. Connected open circles represent the 12 subjects who completed both the six month study periods. For three subjects with incomplete data, filled symbols represent subjects with placebo data only; inverted triangles represent 3 month data. Median values for each phase are shown as horizontal bars.

3. Concise Summary of Project:

This study will be a randomized, double-blind, placebo-controlled, cross-over trial (Fig. 5). Patients who are considered eligible for the study will undergo screening evaluation to determine their eligibility for the trial. For those who are found to be eligible, during the baseline period, they will continue their usual diet and other lifestyle measures without changing any medications for 1 month in order to establish a baseline state. Three blood samples will be obtained during this period at the Clinical and Translational Research Center. Following the baseline period, the patients will receive obeticholic acid (OCA) or an identical placebo in the dose of 25 mg/day for a period of 4 months and then will receive the other treatment (OCA or placebo) for 4 months. There will be a wash-out period of 4 months in-between the two study periods. The dose of OCA is chosen based upon several considerations: a. In a previous study of patients with type 2 diabetes mellitus and hepatic steatosis, this dose resulted in significant improvement in insulin-mediated glucose disposal and reduction in ALT and GGT (49). b. This dose is generally well-tolerated with negligible side effects. If there are intolerable side effects which are considered probably or possibly related to OCA/placebo, the dose of OCA/placebo will be reduced to 25 mg every other day. If the side effects persist despite reduction of the dose, the medication will be stopped but the subject will continue to participate and complete the trial (as per intent to treat protocol).

[figure not shown]

Fig. 5 : Study design and time points for determination of variables. Wash out period will be for 4 months.

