The potential benefit of obeticholic acid therapy is an improvement in hepatic steatosis as demonstrated by ¹H MRS of the liver, as well as possible improvement in raised levels of hepatic enzymes such as transaminases and improved insulin sensitivity. Reduction in hypertriglyceridemia will be shown through improved fasting serum triglyceride levels. The results of this study may help define a safe and effective treatment for non-alcoholic hepatic steatosis in people with lipodystrophy.

13. Biostatistics:

Power and sample size: The primary endpoint variable is the difference in hepatic triglyceride concentration between OCA and Placebo after four months of each treatment. Sample size estimates are based on our preliminary data with a geometric mean hepatic triglyceride concentration of 16% in 29 patients with FPLD who have hepatic triglyceride concentration >5.6% and a corresponding coefficient of variation of 25% based on log transformed data. We expect a reduction in hepatic fat of at least 25% (i.e., reduction from 16% to 12% liver fat with OCA) and calculate, for an alpha of 0.05 and power of >0.90, we will need 16 patients for the study. Allowing for a 20% drop-out rate, a total of 20 patients will be required. The drop-out rate is estimated from our recent studies in patients with FPL (18, 71).

Randomization: The sequence of OCA and placebo treatment will be determined by blocked randomization.

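### The exploratory correlations of OCA-minus-placebo deltas pool the two sequences without adjustment, so a period drift shared by two variables can create or hide an association

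*Combined protocol and SAP*

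**What the plan says.** Section 3 sets the design: "This study will be a randomized, double-blind, placebo-controlled, cross-over trial". Each treatment lasts 4 months, and "There will be a wash-out period of 4 months in-between the two study periods". Section 13 adds that "The sequence of OCA and placebo treatment will be determined by blocked randomization"; the allocation ratio is not given.

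The statistical analysis paragraph of Section 13 describes mixed linear models "to compare OCA versus Placebo after four treatment months and to evaluate treatment sequence effects". A sequence effect is named; a period effect is not. The exploratory analyses then take one difference per patient, OCA minus placebo, for every primary and secondary variable, and "the association among the delta variables will be evaluated with Spearman correlation coefficients". No stratification, centring or partialling by sequence or period is mentioned, and the deltas are not said to come from the mixed models. The next sentence gives the only significance rule: "A two-sided p value of <0.05 will be considered statistically significant". No separate rule is set for exploratory tests.

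**The concern.** In a two-sequence crossover, OCA minus placebo does not mean the same thing in time for every patient. For those who take OCA first it is period 1 minus period 2; for those who take placebo first it is period 2 minus period 1. Any general change over time, for example in weight, diet or the course of the disease, pushes the deltas of one sequence up and those of the other down. If two variables both change over time, their deltas line up by sequence, and the pooled rank correlation picks that up even when the two drug responses are unrelated.

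What is at stake is interpretation. FGF19 is the plan's marker of FXR activation. These correlations are its only patient-level analysis relating the FGF19 response to the responses in liver fat, enzymes and insulin sensitivity. A common time trend could be read as a mechanism, or opposing trends could conceal a real relation.

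**Working it through.** **Inputs from the documents.** 16 evaluable patients and 20 enrolled (Section 13); 4-month treatment periods and a 4-month wash-out (Section 3); planned effect 16% to 12% liver fat; coefficient of variation 25%; two-sided 0.05.

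**Assumptions.** 1:1 allocation (8 and 8), normal deltas, true correlation 0 unless stated. The size of any period shift is not given, so a range is used.

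**Timing.** From the end of period 1 to the end of period 2 is 4 months of wash-out plus 4 months of treatment = 8 months.

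**The plan's sample size.** The plan states "for an alpha of 0.05 and power of >0.90, we will need 16 patients for the study". With d = ln(0.75) = −0.288 and SD = √ln(1 + 0.25²) = 0.246, n = 2 × 0.246² × (1.960 + 1.282)² / 0.288² = 15.4, so 16; and 16/0.8 = 20. This reproduces the figure if the 25% is read as a within-patient CV. The SD of the log delta is then √2 × 0.246 = 0.348 (0.354 if 0.25 is used directly). That reading is needed only to turn SD units into percentages below.

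**Algebra.** Let π be period 2 minus period 1 and τ the drug effect. The expected delta is τ − π for OCA-first patients and τ + π for placebo-first patients. Write k for π divided by the within-sequence SD of the delta. With equal sequences and unrelated responses, the expected pooled Pearson correlation of variables x and y is

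k_x·k_y / √[(1 + k_x²)(1 + k_y²)], which is k²/(1 + k²) for equal shifts.

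At k = 0.3, 0.45, 0.63 and 1 this gives 0.08, 0.17, 0.28 and 0.50. A log transformation does not remove it.

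**Simulation.** At least 20,000 trials per case, 8 patients per sequence, true correlation 0. Pooled Spearman was tested on n − 2 df, and Spearman partialled on sequence on n − 3 df.

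| Shift in x / y (SD of delta) | Pooled mean rho | Pooled p<0.05 | Partialled p<0.05 |
|---|---|---|---|
| 0 / 0 | 0.00 | 5% | 5% |
| 0.3 / 0.1 | 0.03 | 5% | 5% |
| 0.3 / 0.3 | 0.08 | 6% | 5% |
| 0.45 / 0.2 | 0.08 | 6% | 5% |
| 0.45 / 0.45 | 0.17 | 10% | 5% |
| 0.63 / 0.63 | 0.30 | 20% | 5% |
| 1 / 0 | 0.00 | 5% | 5% |
| 1 / 1 | 0.53 | 62% | 5% |
| 1 / −1 | −0.53 | 63% | 5% |

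With 10 per sequence the rates are 25% at 0.63 SD and 74% at 1 SD. A 7/9 split gives almost the same results as 8/8.

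**Masking.** With a true correlation of 0.5 and opposite shifts of 0.75 SD, the pooled mean rho is −0.12; partialled on sequence it is about 0.44.

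**What the shifts mean for liver fat.** At a delta SD of 0.354 log, shifts of 0.3, 0.45 and 0.63 SD are falls of 10%, 15% and 20% between periods (for example exp(−0.63 × 0.354) = 0.80). A shift of 1 SD is a fall of 30% or a rise of 42%. The mapping depends heavily on that SD. A 20% fall shared in SD units by both variables gives a false-positive rate of 51% at SD 0.246, 20% at 0.354, 10% at 0.5 and 6% at 0.693.

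**The case against.** The analysis is labelled exploratory. No endpoint, sample size, success benchmark or stopping rule uses it, and the mixed-model treatment comparisons do not depend on it. That stands, and it sets the weight of the point.

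The documents give no evidence of a period shift. Patients are asked to keep their usual diet and activity and not to change medication without consultation, and a one-month baseline precedes treatment. With staggered enrolment, seasonal effects would largely average out. That also stands: these features make a large common drift less likely, but they do not adjust for one. The wash-out argument in Section 3 concerns carry-over of OCA, which is a different matter.

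From the 62% figure a reader might infer that these correlations are unreliable whatever happens. The documents do not support that. Both variables would have to shift by a full SD, which for liver fat at an assumed SD of about 0.35 log (0.35 against 0.288) exceeds the 25% drug effect the trial is designed to detect.

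A reader might also infer that the correlations are the plan's only evidence on FXR activation. They are not: FGF19 is itself a secondary endpoint compared between OCA and placebo. Nor do the documents say that the deltas are untransformed or computed outside the model; they are silent on how the deltas are obtained.

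Finally, the 5% after adjustment holds only for independent errors. If shared within-patient fluctuation gives a correlation of 0.3 within sequence, the partialled test is significant in about 17% of trials even without any period shift. Adjustment for sequence does not address that.

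**Conclusion.** The point holds as a conditional, minor one. As written, the pooled coefficient carries any period drift common to two variables, and nothing stated in the plan removes it. The size runs from negligible (5–6% false positives when only one variable shifts, or when shifts are small or unequal) to about 10% and 20% when both shift by 0.45 and 0.63 SD of the delta. Higher rates need drift that the documents give no reason to expect. Opposite drifts produce false negative correlations of the same size or mask real ones.

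These figures assume 8 patients per sequence, normal deltas and unrelated responses. The translation into percent liver fat further assumes a delta SD near 0.35 log. The primary and secondary treatment comparisons are unaffected.

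**What to change.** Add one sentence to the exploratory analyses in Section 13: the associations among deltas will be estimated by Spearman correlations partialled on treatment sequence. In SAS this is PROC CORR with the SPEARMAN option and sequence, coded numerically, in the PARTIAL statement, tested on n − 3 degrees of freedom. If deltas are instead centred within sequence before ranking, the p-value should also use n − 3; the ordinary n − 2 gives about 6% false positives rather than 5%.

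The cost is one degree of freedom. At n = 16, a true correlation of 0.5 and no shift, power is about 43–44% against 46% for the pooled version.

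The same sentence should say that adjustment removes the period artefact only. Correlations arising from shared within-patient fluctuation remain, so the results should be reported as descriptive and not as proof of mechanism.
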